9.6. Pharmacodynamics

9.6.1. Glucodynamics

The aim of the euglycemic clamp is to maintain euglycemic through infusion of a 10% to 20% glucose solution after the administration of a dose of insulin. During the euglycemic clamp, the GIR will be adjusted to maintain a predetermined target blood glucose concentration for the individual patients. Thus, blood glucose concentrations are kept constant while the GIR varies, and the varying GIR will reflect the GD activity of insulin.

9.6.1.1. Euglycemic Clamp Procedure

Patients will participate in 2 euglycemic clamps across 2 treatment periods. After at least 8 hours overnight fast, the euglycemic clamp procedure will be performed for approximately 10 hours following administration of a dose of insulin lispro according to the Schedule of Assessments (Section 2) and as described in Section 5.1.

Approximately 1 to 6 hours before the planned administration of study drug, patients will be connected to the clamp device CCI [REDACTED] for continuous blood glucose monitoring and receive a variable IV infusion of either insulin glulisine or glucose to obtain a

steady blood glucose clamp target of 100 mg/dL ($\pm 20\%$) (5.5 [± 1.1] mmol/L). The target blood glucose level of 100 mg/dL (5.5 mmol/L) $\pm 20\%$ (upper and lower limits included) must be kept at -60 to -30 minutes before trial product administration, followed by the target blood glucose level of 100 mg/dL (5.5 mmol/L) $\pm 10\%$ (upper and lower limits included) within the last 30 minutes prior to trial product administration without any glucose infusion. The IV insulin glulisine infusion (if any) is lowered as much as possible to keep the blood glucose concentrations at the target without having to infuse glucose. The insulin glulisine infusion is tapered off and should be stopped 10 minutes [REDACTED] minutes before trial product administration as measured by CCI [REDACTED], and the onset of study insulin action occurs when blood glucose drops to 5 mg/dL (0.3 mmol/L) from baseline. If there are no stable blood glucose measurements with CCI [REDACTED] in the last minutes before intended dosing, dosing should be postponed and the run-in period will be prolonged. If the target blood glucose level cannot be established before 14:00, the visit will be terminated and the patient may be rescheduled for a new dosing visit 1 to 7 days later. After the onset of action has been reached, a variable IV glucose infusion will be initiated in order to keep blood glucose constant at the target level. The GIR necessary to keep the blood glucose concentration at the target level will be recorded using a validated data capture system at the CRU.

The clamp procedure will continue for up to 10 hours after dose or until after blood glucose concentrations increased to >200 mg/dL (11.1 mmol/L) without any glucose being administered for at least 30 minutes, whichever is earlier.

At the end of the clamp procedure, the patient will receive a medical assessment and be given a meal along with their prandial insulin treatment. Their basal insulin regimen may be restarted accordingly, albeit subjected to the stopping guidance as described in Section 5.1, prior to the next dosing visit, if applicable.

9.6.2. Immunogenicity Assessments

Blood samples for immunogenicity testing will be collected to determine antibody production against insulin lispro as described in the Schedule of Activities (Section 2). Additional samples may be collected if there is a possibility that an AE is immunologically mediated.

Immunogenicity will be assessed by a validated assay designed to detect antidrug antibodies in the presence of insulin lispro.

Samples will be retained for a maximum of 15 years after the last patient visit, or for a shorter period if local regulations and ERBs allow, at a facility selected by the sponsor. The duration allows the sponsor to respond to future regulatory requests related to LY900014. Any samples remaining after 15 years will be destroyed.

9.7. Genetics

A blood sample will be collected for pharmacogenetic analysis as specified in the Schedule of Activities (Section 2), where local regulations allow.

Samples will not be used to conduct unspecified disease or population genetic research either now or in the future. Samples will be used to investigate variable exposure or response to LY900014 and to investigate genetic variants thought to play a role in diabetes mellitus. Assessment of variable response may include evaluation of AEs or differences in efficacy.

All samples will be coded with the patient number. These samples and any data generated can be linked back to the patient only by the investigative site personnel.

Samples will be retained for a maximum of 15 years after the last patient visit, or for a shorter period if local regulations and/or ERBs impose shorter time limits, for the study at a facility selected by Lilly. This retention period enables use of new technologies, response to regulatory questions, and investigation of variable response that may not be observed until later in the development of LY900014 or after LY900014 is commercially available.

Molecular technologies are expected to improve during the 15-year storage period and therefore cannot be specifically named. However, existing approaches include whole genome or exome sequencing, genome wide association studies, multiplex assays, and candidate gene studies. Regardless of technology utilized, data generated will be used only for the specific research scope described in this section.

9.8. Biomarkers

This section is not applicable for this study.

9.9. Health Economics

This section is not applicable for this study.

10. Statistical Considerations and Data Analysis

10.1. Sample Size Determination

Up to 40 patients will be randomized in order that approximately 28 patients complete the study. Twenty-eight completing patients will provide approximately 92% power to demonstrate a 40% increase in the insulin lispro area under the concentration versus time curve (AUC) from time zero to 30 minutes ($AUC_{[0-30min]}$) between LY900014 and Humalog. Testing will be done at an alpha level of 0.05 with a 2-sided confidence interval (CI). The variability was estimated by analyzing a Lilly internal study that showed a log-scale standard deviation of within-patient difference in $AUC_{(0-30min)}$ of 0.5. Analysis of internal data showed a log-scale standard deviation of within-patient difference in time to early half-maximal serum concentration (early 50% t_{max}) of 0.5, which provides approximately 95% power to show a 30% reduction in early 50% t_{max} , testing with an alpha level of 0.05 and a 2-sided CI.

In addition, the study is adequately powered to evaluate the GD parameters. There is approximately 71% power to detect a 20% decrease in both time to onset of insulin action (T_{onset}) and time to early half-maximal GIR before time to maximum glucose infusion rate (TR_{max}) (early 50% TR_{max}), and approximately 81% power to detect at least a 40% increase in total amount of glucose infused over 30 minutes ($Gtot_{[0-30min]}$) and total amount of glucose infused over 1 hour ($Gtot_{[0-1h]}$). In estimations, the log-scale standard deviation of within-patient difference was used with 0.45 for T_{onset} and early 50% TR_{max} , and 0.6 for $Gtot_{(0-30min)}$ and $Gtot_{(0-1h)}$.

Patients who discontinue from the study prior to completion of both treatment periods with evaluable primary outcome data can be replaced to ensure that enough patients may complete the study. The replacement patient will adopt the original patient's randomized treatment sequence.

10.2. Populations for Analyses

10.2.1. Study Participant Disposition

A detailed description of patient disposition will be provided at the end of the study.

10.2.2. Study Participant Characteristics

The patient's age, sex, weight, BMI, waist and hip circumference, height, race/subrace, and other demographic characteristics will be summarized.

10.3. Statistical Analyses

Statistical analysis of this study will be the responsibility of Eli Lilly and Company or its designee.

The primary statistical analyses for PK will be conducted on those patients who receive at least 1 dose of study drug and have measurable and evaluable insulin lispro concentrations. The primary statistical analysis for GD will be conducted on those patients who complete at least 1 clamp procedure and have evaluable GD parameters.

Supportive analyses will be done on the key parameters for the patients who complete all treatment periods with evaluable data. Safety analyses will be conducted for all enrolled patients, whether or not they complete all protocol requirements.

Any change in the data analysis methods described in the protocol will require an amendment only if it changes a principal feature of the protocol. Any other change to the data analysis methods described in the protocol and the justification for making the change will be described in the study results.

Summary statistics (including number of patients, mean, standard deviation or standard error, minimum, and maximum) will be presented for continuous variables. A linear mixed-effect model will be used for continuous variables unless otherwise stated in the below subsections. The primary comparison between LY900014 and insulin lispro (Humalog) will be performed using the model that includes treatment, sequence, and period as fixed effects, and patient within sequence as a random effect.

Additional exploratory analyses of the data will be conducted as deemed appropriate. Study results may be pooled with the results of other studies for population PK analysis purposes to avoid issues with post-hoc analyses and incomplete disclosures of analyses.

10.3.1. Safety Analyses

10.3.1.1. Clinical Evaluation of Safety

All investigational product and protocol procedure AEs will be listed, and if the frequency of events allows, safety data will be summarized using descriptive methodology.

The incidence of symptoms for each treatment will be presented by severity and by association with investigational product as perceived by the investigator. Symptoms reported to occur prior to enrollment will be distinguished from those reported as new or increased in severity during the study. Each symptom will be classified by the most suitable term from the medical regulatory dictionary.

The number of investigational product-related SAEs will be reported.

10.3.1.2. Statistical Evaluation of Safety

Safety parameters that will be assessed include safety laboratory parameters, vital signs, and ECG parameters. The parameters will be listed and summarized using standard descriptive statistics. Additional analysis will be performed if warranted upon review of the data.

10.3.1.2.1. Statistical Evaluation of the Intensity of Injection-site Pain

The primary study assessment will be the intensity of pain at each injection site immediately after the injection (time 0) as reported by the patient and measured according to the 0- to 100-mm VAS. A Wilcoxon signed rank test will be used to analyze the time 0 (immediately after dosing) data. A descriptive summary will be provided for the following categories of scores: 0, 1-10, 11-20, 21-30, 31-40, etc. up to the maximum category by treatment for each time point.

10.3.2. Pharmacokinetic Analyses

10.3.2.1. Pharmacokinetic Parameter Estimation

Patients who receive at least 1 dose of study drug and have measurable insulin lispro concentrations will be included in the PK analysis dataset.

The PK analyses will be conducted using standard noncompartmental methods of analysis using CCI [REDACTED] on a computer that meets or exceeds the minimum system requirements for these programs. The version of any software used for the analysis will be documented and the program will meet the Lilly requirements of software validation. It is possible that other validated equivalent PK software programs may be utilized if appropriate, warranted, and approved by global PK management.

Free serum insulin lispro concentrations will be used to calculate several PK parameters, including: early 50% t_{max} , time to late half-maximal serum concentration (late 50% t_{max}), maximum observed concentration (C_{max}), time to maximum observed drug concentration (t_{max}), $t_{1/2}$, AUC from time zero to the last recorded time, AUC_(0-30min), AUC from time zero to 1 hour, AUC from time zero to 10 hours, and AUC from time zero to infinity. Other parameters may be calculated as deemed appropriate. Additional partial AUCs may be computed as necessary. The primary insulin lispro PK parameters for faster insulin lispro absorption analysis are early 50% t_{max} and AUC_(0-30min).

Given the predicted low systemic concentrations of treprostinil, the PK analysis of treprostinil from the LY900014 dosing will be conducted using the available data. The primary analysis of the treprostinil concentrations will be focused on assessing t_{max} and C_{max} .

Although attempts will be made to adhere to the scheduled collection times (Section 2), it is recognized that situations arise that may compromise the scheduled times. Parameters will be individually calculated for each patient based on actual collection times and presented using summary statistics.

10.3.2.2. Pharmacokinetic Statistical Inference

Log-transformed C_{max} and AUC estimates for insulin lispro will be evaluated to estimate least-squares geometric means, ratios of geometric means between LY900014 and Humalog, and their corresponding 95% CIs using the mixed-effects model that includes treatment, sequence, and period as fixed effects and patient within sequence as a random effect.

The same model without log transformation will be used for the analysis of the PK time parameters (early 50% t_{max} , late 50% t_{max} , t_{max} , and $t_{1/2}$). Least-squares means, treatment differences in least-squares means, and the corresponding 95% CIs for the treatment differences will be estimated from the model. The treatment ratios and 95% CIs for the ratios will be calculated using Fieller's theorem.

Statistical significance will be achieved when the p-value for a test is less than 0.05.

The analyses described above will also be performed on the population of patients who completed and had evaluable PK data for both study periods.

As plasma treprostini concentrations after administration of LY900014 are expected to be very low, a descriptive statistical analysis may be conducted if sufficient data are available for this analysis.

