10.3.3. Pharmacodynamic Analyses

10.3.3.1. Glucodynamic Parameter Estimation

Glucodynamic assessments will be determined from the euglycemic clamp procedure, where the GIR over time will be used as a measure of insulin effect. Glucodynamic analyses will be conducted on those patients who complete at least 1 clamp procedure.

A locally weighted scatterplot smoothing (LOESS) function will be applied to all individual GIR versus time profiles in each treatment group and/or period using CCI. The fitted data for each patient will be used to calculate the following GD parameters: maximum GIR (R_{max}), TR_{max} , early 50% TR_{max} , time to half-maximal GIR after TR_{max} (late 50% TR_{max}), T_{onset} , G_{tot} over the duration of the clamp procedure, $G_{tot(0-1h)}$, and $G_{tot(0-30min)}$.

The values of these GD parameters will be summarized by treatment group through descriptive statistics. Mean LOESS fits of GIR versus time profiles will be generated. The primary GD parameters for analysis are early 50% TR_{max} , $G_{tot(0-30min)}$, $G_{tot(0-1h)}$, and T_{onset} .

Additional partial glucose AUCs, such as G_{tot} over 2 hours ($G_{tot[0-2h]}$) and G_{tot} from 3 hours to 10 hours ($G_{tot[3-10h]}$), may be computed as necessary.

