7. SAMPLE SIZE JUSTIFICATION

Up to 40 patients will be randomized in order that approximately 28 patients complete the study. Twenty-eight completing patients will provide approximately 92% power to demonstrate a 40% increase in the insulin lispro area under the concentration versus time curve (AUC) from time zero to 30 minutes (AUC[0-30min]) between LY900014 and Humalog. Testing will be done at an alpha level of 0.05 with a 2-sided confidence interval (CI). The variability was estimated by analyzing a Lilly internal study that showed a log-scale standard deviation (SD) of within-patient difference in AUC(0-30min) of 0.5. Analysis of internal data showed a log-scale SD of within-patient difference in time to early half-maximal serum concentration (early 50% t_{max}) of 0.5, which provides approximately 95% power to show a 30% reduction in early 50% t_{max} , testing with an alpha level of 0.05 and a 2-sided CI.

In addition, the study is adequately powered to evaluate the GD parameters. There is approximately 71% power to detect a 20% decrease in both time to onset of insulin action (T_{onset}) and time to early half-maximal GIR before time to maximum glucose infusion rate (TR_{max}) (early 50% TR_{max}), and approximately 81% power to detect at least a 40% increase in total amount of glucose infused over 30 minutes ($G_{tot}[0-30min]$) and total amount of glucose infused over 1 hour ($G_{tot}[0-1h]$). In estimations, the log-scale SD of within-patient difference was used with 0.45 for T_{onset} and early 50% TR_{max} , and 0.6 for $G_{tot}(0-30min)$ and $G_{tot}(0-1h)$.

Patients who discontinue from the study prior to completion of both treatment periods with evaluable primary outcome data can be replaced to ensure that enough patients may complete the study. The replacement patient will adopt the original patient's randomized treatment sequence.

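### Do two primary PK endpoints, each tested at 0.05 with no rule for combining them, leave the error rate or power of the primary objective misstated?

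*Protocol*

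**What the plan says.** Protocol Section 4 (Table ITRZ.1) sets the primary objective as comparing insulin lispro PK between LY900014 and Humalog, with two endpoints: early 50% tmax and AUC(0-30min). Protocol 10.3.2.1 and SAP 9.3.1 name the same pair as the primary parameters for the analysis of faster absorption.

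Protocol 10.1 and SAP 7 set the level: "Testing will be done at an alpha level of 0.05 with a 2-sided confidence interval (CI". They then give one power statement per endpoint. For AUC(0-30min): "Twenty-eight completing patients will provide approximately 92% power to demonstrate a 40% increase in the insulin lispro area under the concentration" versus time curve over 30 minutes. For early 50% tmax the figure is about 95% for a 30% reduction. Each uses a log-scale SD of the within-patient difference of 0.5.

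Protocol 10.3.2.2 and SAP 9.3.2 call for estimates of treatment differences or ratios with 95% confidence intervals, followed by "Statistical significance will be achieved when the p-value for a test is less than 0.05". Neither document gives a both-required rule, a testing order, an alpha split or a joint power.

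For the secondary glucodynamic (GD) endpoints, Protocol 10.1 says "There is approximately 71% power to detect a 20% decrease in both time to onset of insulin action" and early 50% TRmax, and gives about 81% for the two early Gtot endpoints. Protocol 10.3.3.1 lists these four as the primary GD parameters.

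**The concern.** One question, whether absorption is faster, has two primary endpoints and two tests. If significance on either one is enough, the chance of a false positive somewhere in the pair exceeds 0.05. If both are needed, the power for the objective is neither 92% nor 95% but something lower. The plan does not choose between these readings, so a mixed result, with one endpoint significant and the other not, has no prescribed interpretation. The GD sentence raises a similar worry: taken literally, 71% power for a decrease in both endpoints is a joint claim, and joint power would be lower. What would be at stake is the error rate attached to the headline conclusion and the adequacy of 28 completers.

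**Working it through.** **Inputs.** From Protocol 10.1 and SAP 7: n = 28 completers, two-sided alpha 0.05, and log-scale SDs of the within-patient difference of 0.5 (both PK endpoints), 0.45 (T_onset, early 50% TRmax) and 0.6 (the two Gtot endpoints). Effects are ratios of 1.4, 0.7, 0.8 and 1.4. The documents give no correlation between endpoints. It is assumed here to run from 0 to 0.9, oriented so that benefit on one goes with benefit on the other.

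**Stated powers.** Noncentrality is |ln(ratio)| / (SD/√28). The critical t on 26 df is 2.056. Power comes from the noncentral t distribution.

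| Endpoint | Noncentrality | Power | Stated |
|---|---|---|---|
| AUC(0-30min) | 0.3365/0.0945 = 3.56 | 92.9% | 92% |
| Early 50% tmax | 0.3567/0.0945 = 3.77 | 95.3% | 95% |
| T_onset, early 50% TRmax (each) | 0.2231/0.0850 = 2.62 | 71.4% | 71% |
| Gtot(0-30min), Gtot(0-1h) (each) | 0.3365/0.1134 = 2.97 | 81.5% | 81% |

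All four reproduce as single-endpoint powers. The 71% is therefore the power for each GD time endpoint, in the same way that 81% is the power for each Gtot endpoint.

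**If either PK endpoint could carry a claim.** At correlation 0 the two-sided error is 1 − 0.95² = 9.75%, with an upper bound of 0.05 + 0.05 = 10%. A false result in the direction of faster absorption has probability 0.025 per test, so at correlation 0 the chance of at least one is 1 − 0.975² = 4.9%. The other rows use the bivariate normal distribution.

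| Correlation | Any false rejection | False rejection favouring LY900014 |
|---|---|---|
| 0 | 9.8% | 4.9% |
| 0.5 | 9.1% | 4.5% |
| 0.7 | 8.4% | 4.2% |
| 0.9 | 7.0% | 3.5% |

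About half of the two-sided figure consists of rejections that could not support a claim of faster absorption.

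**If both PK endpoints were required.** Alpha for the pair cannot exceed 0.05. Joint power cannot fall below 0.929 + 0.953 − 1 = 88.2%, whatever the correlation. Simulating paired t-tests at the design effects (200,000 trials per correlation) gives 88.6% at correlation 0, 89.7% at 0.5, 90.6% at 0.7, 91.9% at 0.9 and 92.3% at 0.95. Starting instead from the rounded 92% and 95%, correlation 0 gives 0.92 × 0.95 = 87.4%.

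These joint figures share one limitation. They use a log-scale SD for early 50% tmax, which Protocol 10.3.2.2 and SAP 9.3.2 analyse without log transformation. They indicate size and are not the exact power of the planned pair of tests.

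**GD endpoints.** Read as joint, the T_onset and early 50% TRmax pair would have 0.714² = 51% power at correlation 0 and 61% at 0.7. An any-of-four error would be 1 − 0.95⁴ = 18.5% at correlation 0 and about 13% at 0.7. Neither quantity is one the plan claims.

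**The case for a change.** The best case for a change is that the plan does more than estimate. It sets an alpha, gives power to demonstrate directional effects, and defines when significance is reached. A plan that uses this language could be expected to say which pattern of results answers its primary question, and one sentence would do it. If both endpoints are meant to be required, neither 92% nor 95% is the power for the objective. Changing both to each in the GD power sentence would cost nothing.

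The factual part stands: the rule is absent, and the inflation and the power loss are real under their respective readings. What does not follow is that a stated figure is wrong. The significance sentence concerns a single test. It says nothing about when the objective is met, so the either-endpoint reading is permitted by silence but not prescribed. The two-sided 7% to 10% also overstates the risk of the one error that matters for a claim of faster absorption. The joint power sits at most about 4 points below the 92% using unrounded inputs, and matches it at high correlation. That would not change the sample size. The GD endpoints are secondary, and reading 71% as each endpoint's own power is the natural reading, since only that reproduces.

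**Conclusion.** The concern does not call for a change. The combination rule is missing, but the plan's figures are correct for what they describe: 0.05 per test, and 92%, 95%, 71% and 81% per endpoint. The primary objective is a comparison, in a Phase 1 crossover with no success criterion or go/no-go rule. The planned output is estimates with 95% confidence intervals for each parameter. A mixed result would be reported as two estimates with their intervals, and analysts can do that soundly from the text as it stands.

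Whether to require both endpoints, order them, split alpha or leave the p-values nominal is a choice on which reasonable statisticians differ in this setting. Splitting alpha at 0.025 each would cut power to about 87% for AUC(0-30min) and 91% for early 50% tmax, with no clear gain here. The sponsor could usefully say which reading it intends and write each for both in the sample-size text, but the analysis does not depend on it.

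This conclusion rests on the study remaining an estimation-based PK comparison. The sizes rest on assumed correlations of 0 to 0.9 and, for joint power, on the log-scale SDs in Protocol 10.1.
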